6.15. Temporary Suspension of Enrollment/Drug(s) Dosing or Both

A temporary halt in enrollment will be implemented if an *ad-hoc* DSMB safety review is required. Subjects already on investigational product will continue on therapy unless the *ad-hoc* DSMB review is completed and the DSMB determines that its findings warrant cessation of study drug(s). Subjects in the screening phase of the study may continue to undergo screening procedures.

6.16. Stopping rules

As stated earlier, the progress of the study will be monitored by the DSMB which will review safety data and make recommendations regarding continuation, termination, or modification of the study. Based on a 12 month enrollment period and an additional study period of 12 months, the DSMB will formally review the safety data after participant number 24 reaches day 90 of the study. The number of subjects who discontinue study treatment will also be included in the reports prepared for the DSMB.

In addition, safety data will be reviewed by the DSMB when an event occurs that is of sufficient concern to the medical monitor and/or study investigator(s) to warrant review, or when an event occurs that contributes to a stopping rule listed below.

- **Patient stopping rules:** Subjects who have 3 severe hypoglycemic reactions (requiring assistance from another individual) on separate days or who have nausea or vomiting that precludes adherence to diet will discontinue the use of the study drug. Subjects who lose more than 10 kg will also discontinue study drug. Subjects who discontinue the drug treatment will not be replaced.
- **Trial stopping rules:** Interim analysis will be conducted when recommended by the DSMB to review safety data, including metabolic, immunological assessments and adverse events. The DSMB may recommend early stopping if there is sufficient evidence to conclude that the investigational treatment is harmful based on interim analysis of safety endpoints.

6.17. Potential Benefits

The risks of this study in detailed are presented in the informed consent form. This study will examine whether combination supplement therapy intervention will preserve beta cell function, but there is no guarantee that this will occur.

This is a pilot feasibility trial with the prospect of direct benefit to the individual subjects for their participation in the study. The potential direct benefit to research subjects is that administration of specific combination supplement therapy or vitamin D alone could stabilize or improve β -cell function, thus facilitating attainment of improved glycemic control. All subjects will benefit from being closely involved with an experienced team of diabetes experts, with the likely benefit that their glycemic control will be better than would be otherwise obtained. Thus, these potential benefits include the recognized benefits of being in a clinical study, including close monitoring and additional resources available to maintain tight glycemic control offered to all subjects, regardless of group assignment. These additional resources include frequent in-person and other contact with study associate diabetes educator throughout the duration of the study. Further, the intervention has the prospect of direct benefit to a given subject and is likely to yield general knowledge about T1D which is of importance for the understanding and amelioration of T1D. The study procedures, while greater than minimal risk, offers the possibility of benefit due to the close monitoring for all participants.

If effective in preserving or increasing β -cell function, combination therapy could be an important new treatment to change the course of T1D, thus benefiting the individual research participant and potentially society at large. Moreover, the proposed studies will produce new information about the immune system and its regulation, in the context of T1D and in relation to therapy with these over the counter agents that would be relevant to other autoimmune diseases.

6.18. Pregnancy

Pregnant and lactating women will not be included in the study. Sexually active females must have a negative pregnancy test prior to enrolling in the study and will be required to use at least two FDA approved birth control during the study. At every study visit the sexual activity of female participants of reproductive age will be re-assessed. If a subject who was previously sexually inactive becomes sexually active, she will be counseled about the need to use a reliable forms of birth control. Subjects will be requested to avoid pregnancy for 6 months following the last study administration and instructed to use birth control.

6.19. Protecting Against or Minimizing Potential Treatment Risks

Subjects will not be enrolled who have other active serious medical problems. Frequent monitoring of patients with history, physical examination, and laboratory studies will allow for early identification of adverse events. All participants will be required to have adequate hemoglobin to allow frequent venipuncture. The supplement drugs will be dispensed to subjects free of cost, and subjects will be closely monitored during and after the treatment.

Subjects will be counseled about the potential risk for gastrointestinal side effects and the need to report any change in health status between or at the time of visits. Directed questioning about concurrent illness will occur before each treatment.

6.20. Supplement - Drug Interaction

Vitamin D

Like most dietary supplements, vitamin D may interact or interfere with other medicines or supplements.. Here are several examples:

- Corticosteroid medicines to reduce inflammation impair how the body handles vitamin D, which leads to lower calcium absorption and loss of bone over time.
- Both the weight-loss drug orlistat (brand names Xenical® and Alli®) and the cholesterol-lowering drug cholestyramine (brand names Questran®, LoCholest®, and Prevalite®) can reduce the absorption of vitamin D and other fat-soluble vitamins (A, E, and K).
- Both phenobarbital and phenytoin (brand name Dilantin®), used to prevent and control epileptic seizures, increase the breakdown of vitamin D and reduce calcium absorption.

Omega-3 Fatty Acids

Omega-3 Fatty Acids can affect medications that influence blood clotting phenomenon, some of which includes:

- Antiplatelet Medication: Anagrelide (Agrylin®), aspirin(any brand, all doses), cilostazol (Pletal®), clopidogrel (Plavix®), dipyradamole (Persantine®), dipyridamole/aspirin (Aggrenox®), enteric-coated aspirin (Ecotrin®), ticlopidine (Ticlid®)
- Anticoagulant Medication: Anisindione (Miradon®), Arixtra, enoxaparin (Lovenox®) injection, Fragmin, heparin injection, Pradaxa, pentosan polysulfate (Elmiron®), warfarin (Coumadin®), Xarelto
- Nonsteroidal Anti-Inflammatory Drugs: Celebrex, diclofenac (Voltaren®, Cataflam®), diflunisal (Dolobid®), etodolac (Lodine®), fenoprofen (Nalfon®), flurbiprofen (Ansaid®), ibuprofen (Motrin®, Advil®, Nuprin®, Rufen®), indomethacin (Indocin®), ketoprofen (Orudis®, Actron®), ketorolac (Toradol®), meclofenamate (Meclofenamate®), meloxicam (Mobic®), nabumetone (Relafen®), naproxen (Naprosyn®, Naprelan®, Aleve®), oxaprozin (Daypro®), piroxicam (Feldene®), salsalate (Salflex®, Disalcid®), sulindac (Clinoril®), sulfinpyrazone tolmetin (Tolectin®), trilisate (salicylate combination)
- Herbs/Vitamins: Ajoene, birch bark, cayenne, Chinese black tree fungus, cumin, evening primrose oil, feverfew, garlic, ginger, ginkgo biloba, ginseng, grape seed extract, milk thistle, onion extract, St. John's wort, turmeric, vitamins C and E.

The study team will evaluate the list of all medications and its interaction with Vitamin D or Omega-3 Fatty Acids dietary supplements patients take. Study team will educate and may alter medical treatment

if dietary supplements might interact or interfere with their prescription or over-the-counter medicines, or if the medicines might interfere with how patients body absorbs, uses, or breaks down nutrients.

7. ADVERSE EVENT REPORTING AND SAFETY MONITORING

7.1. Adverse Event Definition

7.1.1. Adverse Event (AE)

In this clinical study, an adverse event is any occurrence or worsening of an undesirable or unintended sign, symptom or disease whether or not associated with the treatment and study procedures.

Throughout the study, the investigator must record all adverse events on source documents. Events not related to hypo or hyperglycemia that are Grade 2 or greater per the NCI CTCAE (see Grading Event Severity below) will be reviewed by study physician and medical monitor on the appropriate adverse event form. The investigator will treat participants with adverse events appropriately and observe them at suitable intervals until the events resolve or stabilize.

Adverse events may be discovered through:

- observation of the participant;
- questioning the participant;
- unsolicited complaint by the participant

In questioning the participant the questioning should be conducted in an objective manner.

7.1.1.1. Disease specific AE

For the purposes of this study, hypoglycemia events will be recorded as follows:

- Level 1: glucose < 70 mg/dl (3.9 mmol/l) and glucose ≥ 54 mg/dl (3.0 mmol/l), and
- Level 2: glucose < 54 mg/dl (3.0 mmol/l)
- Level 3: a severe event characterized by altered mental and/or physical status requiring assistance.
- . Level 2 and Level 3 hypoglycemic events must be reported as adverse events on the case report forms. *All episodes of Level 3 hypoglycemia will be reported as SAEs to the DSMB.*

Hypoglycemia grading according to CTCAE version 4.0

Adverse Event	Grade 1	Grade 2	Grade 3	Grade 4	Grade 5
Hypoglycemia	<LLN-54mg/dL	<54 -40 mg/dL	<40-30 mg/dL	<30 mg/dL; life threatening consequences; seizures	Death

Hyperglycemia will not be collected as an adverse event, unless it results in an inpatient hospitalization.

7.1.2. Serious Adverse Event

For this trial, an adverse event associated with the treatment or study procedure that suggests a significant hazard, contraindication, side effect or precaution (as described below) is to be reported as a serious adverse event (SAE). A serious adverse event (experience) or reaction is any untoward medical occurrence that:

- results in death,
- is life-threatening,
- requires inpatient hospitalization or prolongation of existing hospitalization,
- results in persistent or significant disability/incapacity, or
- is a congenital anomaly/birth defect.

Important medical events that may not result in death, be life threatening, or require hospitalization may be considered serious adverse events when, based upon appropriate medical judgment, they may jeopardize the patient and may require medical or surgical intervention to prevent one of the outcomes listed above.

7.1.3. Unexpected Adverse Event

An adverse event is considered unexpected when the nature (specificity) or severity of the event is not consistent with the risks described in the protocol or informed consent document for a particular protocol.

7.1.4. Grading Event Severity

This study will adopt the National Cancer Institute (NCI) Common Technology Criteria for Adverse Events (CTCAE) and/or study-specific criteria for classification to describe the severity of adverse events with the exception of hyper and hypoglycemia. For this study, a reportable hypoglycemic event is defined as Level 3 (a severe event characterized by altered mental and/or physical status requiring assistance) and hyperglycemic event is one resulting in Diabetes Keto Acidosis (DKA).

7.1.5. Evaluation of Adverse events

A non-serious adverse event is an AE not classified as serious. Both serious and non-serious AEs should be graded with respect to severity on the following 3 point scale and reported, in detail, on the appropriate CRF page:

Mild	Discomfort noticed, but no disruption of normal daily activities; event usually requires no intervention.
Moderate	Discomfort sufficient to reduce or affect normal daily activities; even may require intervention.
Severe	Incapacitating, with inability to perform normal daily activities; event usually requires treatment or other intervention. Subject may not be able to continue in the study.

The Investigator should evaluate the relationship of each AE to the study treatment regimen, using the following criteria:

Unrelated:	Another cause of the AE is more plausible; a clinically plausible temporal sequence is inconsistent with the onset of the AE and administration of the study treatment regimen; or a causal relationship is considered biologically impossible.
Possibly related:	There is a clinically plausible time sequence between onset of the AE and administration of the study treatment regimen, but the AE could also be attributed to concurrent or underlying disease, or the use of other drugs or procedures. "Possibly Related" should be used when the study treatment regimen is one of several biologically plausible AE causes.
Definitely Related:	The AE is clearly related to use of the study treatment regimen.

7.1.6. Adverse Event Reporting and Monitoring

Study personnel will assess adverse events and the use of concomitant medications throughout the study. They will be graded as to severity according to common toxicity criteria or study-specific criteria and the investigator will make a determination as to the relation to therapy. Events will be assessed and reported in accordance with the ICH Guideline for Good Clinical Practice and per the guidance of the DHHS Office for Human Research Protections (OHRP). The adverse event case report for the protocol must be documented for all adverse events (AE) of Grade 2 or greater severity regardless of relationship to therapy. For reporting serious adverse events (SAE), the MedWatch Form should also be completed and sent to medical monitor *within 24 hours of when the site was notified of the event*. This will be reviewed by the study physicians and Medical Monitor, and the Data and Safety Monitoring Board (DSMB) as appropriate. Deaths must be reported immediately. Event outcome and other follow-up information regarding the treatment and resolution of the event will be obtained and reported when available, if not known at the time the event is reported. The follow-up information should contain sufficient detail to allow for a complete medical assessment of the case and an independent determination of possible causality.

Adverse events will be assessed by the Medical Monitor. The DSMB will conduct regular safety reviews approximately every three to six months (and, as needed) of adverse events by treatment group

assignment. Serious adverse events as well as adverse events leading to treatment discontinuation will be reviewed by the DSMB.

Fatal or life-threatening events thought to be caused by study drug(s) should be reported to the Medical Monitor, or CRA immediately, as follows:

Position	Name	Telephone Number	Pager Number
Medical Monitor	[name] M.D., FACS Professor of Surgery Director, Division of Kidney and Pancreas Transplantation, [name] Email: [contact]	[contact]	[contact]
CRA	Clinical Research Operations & Regulatory Support (CRORS), Miller Office of Research, University of Miami, Miller School of Medicine, [name]	[contact]	[contact]

7.1.7. Recording Adverse Events

To improve the quality and precision of AE data, **Investigators should observe the following guidelines:**

- Whenever possible, use recognized medical terms when recording AEs on the AE page of the CRF. Do not use colloquialisms, jargon, or abbreviations.
- If known, record the diagnosis (ie, disease or syndrome) rather than component signs and symptoms on ae pages of the CRF (eg, record “congestive heart failure” rather than “dyspnea”, “rales”, and “cyanosis”). However, signs and symptoms that are considered unrelated to an encountered syndrome or disease should be recorded as individual AEs on the CRF page. For example, if congestive heart failure and severe headache are observed at the same time, each event should be recorded as an individual AE.
- Adverse events occurring secondary to other events (ie, sequelae) should be identified by the primary cause. A primary ae, if clearly identifiable, generally represents the most accurate clinical term to record on ae pages of the CFR. If a primary SAE is recorded on an AE CRF page, events occurring secondary to the primary event should be described in the narrative description of the event.
- Laboratory abnormalities that are defined as clinically significant are to be considered AEs and recorded on the AE CRF page.

7.1.8. Adverse Events Requiring Expedited Reporting

Serious AEs require expedited reporting to the Sponsor or designee, regardless of the relationship of the event to the study treatment regimen. Refer to the previous section for the definition of a serious adverse event.

Investigators should report all SAEs to the Sponsor or designee within 24 hours of the observation or learning of the event. For initial SAE reports, the Investigator should record all case details that can be garnered on the SAE form and the AE CRF page.

The completed SAE form and Cover Sheet should be faxed within 24 hours to the medical monitor at [contact] or via email [contact]. Relevant follow-up information is to be submitted to the Sponsor or its designee as soon as it becomes available.

7.1.9. Special Reporting Situations

Death: Death is an outcome of an event. The event that resulted in death should be recorded and reported on the SAE form and the AE CRF page.

Hospitalization for Surgical or Diagnostic Procedures: The illness leading to the surgical or diagnostic procedure is to be recorded as the SAE, not the procedure itself. The procedure is to be captured in the case narrative as part of the action taken in response to the illness.

7.1.10. Laboratory Test Result Abnormalities

The following laboratory test result abnormalities should be captured on the non-serious AE CRF page or SAE Report Form (paper or electronic) as appropriate:

- Any laboratory test result that is clinically significant or meets the definition of an SAE
- Any laboratory test result abnormality that required the subject to have study drug discontinued or interrupted
- Any laboratory test result abnormality that required the subject to receive specific corrective therapy.

It is expected that wherever possible, the clinical rather than laboratory term would be used by the reporting investigator (e.g. anemia versus low hemoglobin value).

7.1.11. Pregnancy

If, following initiation of the study product(s), it is subsequently discovered that a study subject is pregnant or may have been pregnant at the time of investigational product exposure, including up to 12 weeks after last product administration, the study product(s) will be permanently discontinued in an appropriate manner (e.g. dose tapering if necessary for subject safety).

They must be reported to the medical monitor within 24 hours by fax to [contact] with a confirmatory telephone call to [contact] and in accordance with SAE reporting procedures described above.

Any pregnancy that occurs in a female partner of a male study participant should be reported to the medical monitor.

7.1.12. Overdose

All occurrences of overdose must be reported as SAEs (see SAE reporting section for details).

An overdose is defined as the accidental or intentional administration of any dose of a product that is considered both excessive and medically important. All occurrences of overdose must be reported as an SAE.

7.1.13. Other Safety Considerations

Any significant worsening noted during interim or final physical examinations, electrocardiogram, x-ray filming, any other potential safety assessment required or not required by protocol should also be recorded as a non-serious or serious AE, as appropriate, and reported accordingly.

8. DATA QUALITY ASSURANCE

Accurate, consistent, and reliable data will be ensured through the use of standard practices and procedures. These are described in the following sections.

8.1. Data Collection, Monitoring, and Transfer

Adverse events will be collected from the initiation of study drug and be followed to resolution or until 30 days after the participant completes participation, whichever comes first.

Adverse events may be collected as follows:

- Observing the participant.
- Questioning the participant in an objective manner.
- Receiving an unsolicited complaint from the participant.

An abnormal value or result from a clinical or laboratory can also indicate an adverse event. If this is the case, then the evaluation that produced the value or result should be repeated until the value or result returns to normal or can be explained and the participant's safety is not at risk. If an abnormal value or result is determined by the investigator to be clinically significant, it must be indicated as such on the appropriate laboratory evaluation form(s), and must also be reported as an adverse event on the adverse event form. Abnormal vital sign measurements or laboratory finding deemed not clinically significant by the site investigator must be documented as such and are not required to be listed in the

adverse event source documents or adverse event case report form. The DRI will perform data collection, monitoring, and transfer tasks. A Clinical Research Monitor designated by Sponsor will be responsible for monitoring the clinical study in accordance with current federal and relevant foreign regulations. The Monitor will periodically collect the CRFs and brought them to Sponsor. Data on CRFs will be double-entered into the database system and verified.

8.2. Quality Control and Quality Assurance

The database will be verified against the CRFs as outlined in the monitoring plan.

9. STATISTICAL CONSIDERATIONS AND ANALYSIS PLAN

9.1. Overview

This study will test the hypothesis that combination therapy, administered for one year to patients with either new onset or established T1D with residual stimulated C-peptide, will retain C-peptide secretion compared to therapy with vitamin D alone.

9.2. Endpoints/Outcomes

Primary endpoint:

- Stimulated (90 minute sample of a MMTT) C-peptide at the 1 year visit greater or equal to baseline level.

Secondary Objective(s)

- Stimulated C-peptide area under the curve during a 4-hour MMTT greater or equal to baseline level, at the 1 year visit.
- Reduction in HbA1c at the one year visit compared to baseline.
- Reduction in insulin requirement at the 1 year visit compared to baseline.
- Incidence of adverse events (AE) comparable to general diabetes population.

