9.4.1. Analysis Populations

Analyses of study data will be conducted to address all objectives of the trial and other interrelationships among data elements of interest to the investigators and of relevance to the objectives of the study. Primary analysis of treatment effect will be conducted under the intention-to-treat principle of eligible patients whereby outcome data from all eligible patients will be included regardless of treatment compliance.

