9.4.2. Primary Analysis of Primary Endpoint(s)/Outcome(s)

The metabolic primary outcome is the 90-minute stimulated C-peptide following MMTT, conducted at the 1 year visit. The primary statistical hypothesis to be assessed is that the proportion of patients with maintained or increased level of 90-minute at 12 months as compared to baseline will be greater in subjects receiving combination therapy than for subjects receiving vitamin D alone.

The analysis of the primary outcome will initially involve a two sample test of proportions comparing the proportion of patients in the combination therapy group maintaining or increasing 90-C-peptide with respect to baseline with the proportion of vitamin D alone treated subjects with 90-minute C-peptide that is maintained or increased from baseline value. A covariate-adjusted analysis will additionally be performed by way of a logistic regression model, with a categorical index of treatment group adjusted for baseline age and time since diagnosis; this can provide us with adjustment for potential confounding of these factors and/or provide increased efficiency and precision by including these potentially significant explanatory variables.

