9.4.3. Supportive Analyses of the Primary Endpoint(s)/Outcome(s)

90-min C-peptide measured at screening and , 12 months and 24 months in the different treatment groups will additionally be fit to a mixed linear regression model, allowing estimation and testing of means and differences between groups at each time point, while simultaneously accommodating the correlation arising from the longitudinal study design in estimates of variances used in tests of significance. We will also estimate and test the differential rate of change in mean 90-min C-peptide over time between these groups, by incorporating an interaction term between time point and treatment group into the models. Although this investigation is not specifically powered to test this interaction, this might provide us with useful insight as to the differences in the effect of combination therapy over time on 90-min C-peptide.

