9.4.4. Descriptive Analyses

In addition to the detailed statistical analysis described above, descriptive analysis will include reporting and comparison baseline characteristics of the study subjects to evaluate whether any substantial differences exist between the vitamin D alone and combination treatment groups for key variables such as age, gender, BMI, HbA1c, baseline C-peptide, insulin requirements and other variables such as concomitant use of other medications to determine any potential bias. These will involve standard two sample comparisons such as T-tests for continuous variables (possibly transformed when necessary to preserve distributional assumptions) and Chi-square or Fisher's exact tests for categorical variables. As described earlier, potentially confounding factors arising from imbalance will be included into more formal statistical models of the investigation.

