9.5.3. Futility Analysis

Futility is unlikely to be shown during a one year treatment period, but the DSMB can decide to terminate the study should futility be shown. We do not intend to stop the study for futility as we intend to obtain an estimate and 95% confidence interval for the effect of treatment between groups at the 1 year mark

using the full information offered by our design. Additionally, not stopping for futility incorporates the consideration that the C-peptide AUC curves of combination therapy and vitamin D alone groups may separate later on follow-up, as AUC values decline further in the vitamin D alone group. Essentially all type 1 diabetes trials have been allowed to reach their one-year endpoint, even those that showed no efficacy.

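### The first-listed secondary endpoint, 4-hour C-peptide AUC, is defined only as at or above own baseline, and no between-arm analysis of it is specified

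*Combined protocol and SAP*

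**What the plan says.** The AUC endpoint is worded the same way in section 1.1 (Objective), section 4.2.2 and section 9.2: "Stimulated C-peptide area under the curve during a 4-hour MMTT greater or equal to baseline level, at the 1 year visit". It is the first of four secondary items, which are not ranked. Nowhere is it given as a level, a change or a ratio, and none of the three places mentions a comparison between arms.

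The analysis sections name other variables:

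- Section 9.4.2 deals with the 90-minute value: "The analysis of the primary outcome will initially involve a two sample test of proportions", followed by a logistic model.
- Section 9.4.3 fits a mixed linear model to 90-minute C-peptide at screening, 12 and 24 months: "We will also estimate and test the differential rate of change in mean 90-min C-peptide over time between these groups".
- Section 9.4.4 concerns the arms at entry: "descriptive analysis will include reporting and comparison baseline characteristics of the study subjects".
- Sections 9.6 and 9.7 state hypotheses and sample size for the 90-minute responder rate alone.
- Section 9.4.1 makes a general promise: "Analyses of study data will be conducted to address all objectives of the trial". It gives no variable, contrast, model or time point for AUC.

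AUC reappears in section 9.5.3, which argues against stopping for futility. After a first reason (an estimate and 95% CI at one year), it adds that "the C-peptide AUC curves of combination therapy and vitamin D alone groups may separate later on follow-up".

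**The concern.** Two things do not fit together. The endpoint reduces a multi-sample measure of beta-cell secretion to one binary result against the participant's own baseline. Section 9.5.3 thinks of the same measure as a pair of curves that may diverge between arms during follow-up, which is a continuous between-arm comparison. No specified analysis makes that comparison, either at month 12 or at month 24. The 90-minute value has a continuous longitudinal model; AUC does not.

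Two things are at stake. The first is precision: a binary cut discards information that a trial of 56 participants can ill spare, unless the effect is very large. The second is prespecification: the trial is open label, and with no stated AUC variable, scale or contrast, the choice stays open until data have been seen.

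**Working it through.** **Inputs from the documents**

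- Enrolment is 56, allocated 1:1, so 28 per arm (section 4.6).
- Section 9.7 allows 10% missing: 28 × 0.90 = 25.2, so about 25 evaluable per arm.
- Section 9.7 assumes 5% against 50% for the 90-minute responder rate.
- Section 4.3 uses the screening MMTT as baseline, and the Schedule of Events marks a 4-hour MMTT at visits 0, 4 (month 12) and 7 (month 24).

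**Assumptions, because the documents are silent**

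- No SD, expected effect or responder rate is given for AUC. I take the change in AUC as normal with equal SD in both arms, control responder rates from 5% to 50%, and shifts of 0.5, 0.8 and 1.0 SD.
- No efficacy alpha is stated; I use two-sided 0.05.

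**Step 1. The plan's only figure.** For 5% against 50% at 80% power and alpha 0.05, the pooled formula gives 12 per group one-sided and 15 two-sided. The unpooled two-sided formula gives 11.5, rounded up to 12. So the stated 12 reproduces, but it concerns the 90-minute responder comparison. There is no stated figure for AUC.

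**Step 2. Information kept by the cut.** For a normal change cut at zero with responder rate p, the asymptotic efficiency relative to the continuous change is φ(z_p)² / [p(1 − p)].

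| p | φ(z_p) | Efficiency | 1 / efficiency |
|---|---|---|---|
| 5% | 0.1031 | 0.0106 / 0.0475 = 0.22 | 4.5 |
| 20% | 0.2800 | 0.0784 / 0.16 = 0.49 | 2.0 |
| 50% | 0.3989 | 0.1592 / 0.25 = 0.64 | 1.6 |

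The 5% row uses the control rate that section 9.7 assumes for 90-minute C-peptide; carrying it over to AUC is an assumption.

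**Step 3. Power at 25 per arm.** The continuous column is a two-sample t-test (noncentral t). The others are a chi-square test on change at or above zero, by exact binomial enumeration, with active-arm rate Φ(z_p + shift).

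| Shift | Continuous | Cut, p = 5% | 10% | 20% | 30% | 50% |
|---|---|---|---|---|---|---|
| 0.5 SD | 41% | 14% | 21% | 27% | 31% | 31% |
| 0.8 SD | 79% | 38% | 50% | 59% | 65% | 60% |
| 1.0 SD | 93% | 59% | 71% | 80% | 83% | 77% |

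**Step 4. The plan's own large effect.** Under normality, 5% against 50% is a shift of 0 − (−1.645) = 1.645 SD. At 25 per arm the cut version then has 98% power by chi-square and 95% by Fisher's exact test, against more than 99.9% for the t-test. At that size the loss is small.

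**Step 5. Is a month-24 AUC available?** The Schedule of Events marks the 4-hour MMTT at visit 7. In Appendix B the visit-7 total is 33.8 mL. The other samples alone give 1.8 + 3.5 + 21 + 2 + 3.5 + 2 = 33.8 mL. With the 38.5 mL MMTT the total would be 72.3 mL. The visit-4 total of 77.8 mL does include it: 2 + 1.8 + 3.5 + 3.5 + 21 + 2 + 38.5 + 3.5 + 2 = 77.8. Rows of this table may have been damaged in reading, but the printed totals point the same way. The two appendices have to be reconciled before a month-24 AUC analysis can be counted on.

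**The case against.** The strongest case on the other side is that this is an unranked secondary outcome in a pilot trial, cut the same way as the primary, and that the real gap is wider: HbA1c and insulin requirement also lack a specified between-arm method. That stands. It widens the gap without closing it for AUC.

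It can also be said that later separation in C-peptide is already covered, because section 9.4.3 will test the "differential rate of change in mean 90-min C-peptide over time between these groups" using a sample from the same meal test. This stands in part: secretion is not left to a dichotomy alone. But it is a single time point, not the AUC that section 9.5.3 names.

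The general promise in section 9.4.1 means one cannot say that AUC will go unanalysed, only that no between-arm analysis is specified.

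A reader might infer that the decision to run on rests on AUC. Section 9.5.3 does not support that. AUC separation is a hedged addition to the one-year estimate and confidence interval, and a further reason follows, that similar trials have been allowed to reach one year. Without the AUC clause the decision would be the same.

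A reader might also infer that 25 per arm cannot bear the loss from the cut. Step 4 shows otherwise for an effect as large as the plan assumes for its primary endpoint.

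**Conclusion.** The point holds as headed. The AUC endpoint is binary against own baseline in all three places where it is defined, no between-arm analysis of it is specified, and section 9.5.3 refers to a contrast that the plan does not undertake to estimate.

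The cut keeps about 22% to 64% of the information. This matters for moderate effects: at 0.8 SD and 25 per arm, about 79% power falls to 38% to 65%. It matters little for effects near 5% against 50%. The efficiencies are asymptotic, and all these figures assume a normal change with equal SD and borrowed responder rates, so they show direction and rough size only. The documents make no power claim for AUC, so none is contradicted.

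This should be changed, because a more precise analysis is available at little cost. It does not threaten the primary analysis.

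**What to change.** Define the AUC endpoint as the between-arm difference in month-12 4-hour AUC, analysed as a continuous variable on a prespecified scale (for example log, though untransformed AUC or change would also serve). Adjust for screening AUC and the two randomisation strata in section 5.2 (new or established disease, child or adult), and report the estimate with a 95% CI. Keep the proportion at or above baseline as descriptive.

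Fit the same contrast at month 24, so that the separation mentioned in section 9.5.3 is estimated. First reconcile the Schedule of Events with the visit-7 total in Appendix B.

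The cost is SAP wording and one more model. The month-12 test is already scheduled; month 24 depends on the reconciliation. The small downside is that the AUC result is reported mainly as a mean difference or ratio instead of a responder proportion.
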